6.5. Study Drug Compliance

For participants in the safety and the extension evaluable populations, the overall compliance (%) for povorcitinib/placebo will be calculated as follows:

Compliance (%) = $100 \times [\text{total dose actually taken in the specific period}] / [total prescribed dose in the specific period].$

The total prescribed dose in the specific period is defined as the sum of the doses prescribed by the investigator accounting for dose interruptions during the specific period; this will be calculated as follows:

[Duration of treatment with study drug in the specific period – number of days with dose interruptions in the specific period] \times 5 (tablets/day).

The total actual dose taken in a specific period will be calculated as follows:

Total number of tablets dispensed in the specific period – total number of tablets returned in the specific period.

For more details on the total number of tablets dispensed and returned, see Section 6.4.

6.6. Prior and Concomitant Medication

Prior medications and concomitant medications will be coded using the WHO Drug Dictionary. For the ITT population in the PC period, both prior and concomitant medication will be summarized by treatment group and overall. For the extension evaluable population in the extension period, only concomitant medications will be summarized by treatment group and overall. For participants who took only povorcitinib 45 or 75 mg during the overall period, concomitant medications will be summarized by treatment group and overall. The number and percentage of participants in all populations will be summarized by WHO drug class and WHO drug preferred term.

7. EFFICACY

Appendix A provides a list of data displays. Sample data displays are included in a separate document.

7.1. General Considerations

All by-visit analyses for the extension evaluable population will include the follow-up period, if the data are available or unless otherwise specified. Likewise, unless otherwise stated, the strata identified in the randomization process will be used in all efficacy analyses.

7.2. Efficacy Parameters

7.2.1. Investigator's Global Assessment

The IGA for chronic prurigo considers the number of pruriginous lesions, which includes papules, nodules, plaques, umbilicated ulcers and ulcers to rate the overall severity on a scale of 0 to 4 (Zeidler et al 2021; see Table 5). The nodular rating will be performed at scheduled visits.

The IGA-TS is defined as an IGA score of 0 or 1 with $a \ge 2$ -grade improvement from baseline.

Grade	Severity	Description
0	Clear	No nodules (0 nodules)
1	Almost clear	Rare palpable pruriginous nodules (approximately 1-5 nodules)
2	Mild	Few palpable pruriginous nodules (approximately 6-19 nodules)
3	Moderate	Many palpable pruriginous nodules (approximately 20-100 nodules)
4	Severe	Abundant palpable pruriginous nodules (over 100 nodules)

Table 5:Investigator's Global Assessment

7.2.4. Patient-Reported Outcomes

Patient-reported outcomes and quality of life will be assessed using the following tools:

7.2.4.1. Itch Numerical Rating Scale

Each evening, participants will assess their worst level of itch during the past 24 hours on a scale of 0 (no itch) to 10 (worst itch imaginable) via a handheld device (eDiary).

The baseline Itch NRS score will be determined by averaging the 7 daily Itch NRS scores before Day 1 (ie, Day -7 to Day -1). Should ≥ 4 of the 7 days of the daily Itch NRS scores be missing prior to Day 1, then the baseline Itch NRS will be set to "missing."

The by-visit Itch NRS score for postbaseline visits will be determined by averaging the 7 daily Itch NRS scores before the visit day. If 4 or more daily Itch NRS scores out of the 7 days before the visit day are missing, the Itch NRS at the visit will be set to missing.

The most appropriate threshold for defining a clinically relevant, in-person response is \geq 4-point reduction relative to baseline (Kimball et al 2016).

For time to \geq 4-point improvement from baseline in Itch NRS score, 3-day smooth moving average (SMA) method will be used. For each Day X (X = 2 to two days before the first dose date in extension period for participants who entered extension period, or one day before discontinuation date for participants who discontinued PC period), a SMA value is calculated as the average of daily Itch NRS scores on Day X – 1, Day X, and Day X + 1. If 1 or more daily Itch NRS scores out of the 3-day interval are missing, the SMA value for the day will be set to missing. The first day achieving \geq 4-point improvement from baseline in daily Itch NRS score is defined as the day with both the value at the day, and its SMA value are \geq 4-point lower as compared to the baseline Itch NRS score defined above. Then the time to \geq 4-point improvement from baseline in Itch NRS score will be calculated as:

(Date of first day achieving \geq 4-point improvement from baseline in daily Itch NRS score – Day 1 date +1).

Participants who did not achieve \geq 4-point improvement from baseline in Itch NRS score during the PC period will be censored as follows:

- Participants who completed the PC treatment period through Week 16 without having the event will be censored at one day before the first dose date in extension period, and the censored time will be calculated as: (Date of one day before the first dose date in extension period Day 1 date +1)
- Participants who discontinued during the PC period without having the event will be censored at the date of discontinuation in PC period, and the censored time will be calculated as: (Date of discontinuation in PC period Day 1 date +1).

VV-CLIN-023817

CONFIDENTIAL

VV-CLIN-023817

CONFIDENTIAL

7.3. Efficacy Hypotheses

The primary hypothesis is that povorcitinib 75 mg is superior to placebo in proportion of participants achieving \geq 4-point improvement in Itch NRS at Week 16. If the response rates of achieving \geq 4-point improvement in Itch NRS at Week 16 in the povorcitinib 75 mg and placebo groups are denoted as p_T and p_C , respectively, then the primary hypotheses of the study are as follows:

- H_0 (null hypothesis): $p_T = p_C$
- H_A (alternative hypothesis): $p_T \neq p_C$

7.4. Analysis of the Primary Efficacy Parameter

The primary efficacy endpoint is the proportion of participants achieving \geq 4-point improvement in Itch NRS at Week 16.

7.4.1. Primary Efficacy Analysis

The primary efficacy analysis will compare povorcitinib 75 mg versus placebo in the proportion of participants achieving \geq 4-point improvement in Itch NRS score at Week 16 using an exact logistic regression (Mehta and Patel 1995) based on the ITT population. This model will include the treatment groups (placebo and povorcitinib 15, 45, and 75 mg) and stratification factor (Day 1 IGA score [3 or 4]). The unadjusted p-values between each of the povorcitinib groups and the placebo group will be compared at 2-sided $\alpha = 0.05$ in a fixed sequence from high dose to low dose (75 mg vs placebo \rightarrow 45 mg vs placebo \rightarrow 15 mg vs placebo); the lower dose will be tested only if the null hypothesis associated with the higher dose is rejected. The estimated odds ratios and corresponding 95% CIs will be provided as well. All observed nonresponders, as well as all participants who discontinue study treatment, withdraw from the study for any reason at any time before the timepoint of interest (ie, Week 16), or those participants that do not have the postbaseline assessment at the timepoint of interest, will be defined as nonresponders for the NRI analysis. All participants who receive rescue therapy during the placebo-controlled period will be imputed as nonresponders for all subsequent visits after the initiation date of rescue therapy.

The number of participants achieving \geq 4-point improvement in Itch NRS score at Week 16 and the respective rates, as well as the 2-sided 95% exact CIs, which are based on the Clopper-Pearson method, will be presented by treatment group.

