5.1. Inclusion Criteria

Participants are eligible to be included in the study only if all of the following criteria apply:

- 1. Ability to comprehend and willingness to sign a written ICF for the study.
- 2. Men and women 18 to years of age.
- 3. Clinical diagnosis of PN for at least 3 months before screening.

Note: Diagnosis may be based on investigator assessment and study participant interview.

4. Inadequate response or intolerant to ongoing or prior PN therapy.

Note: Previous PN therapy may include any treatment (including over-the-counter products) intended to treat PN symptoms.

5. \geq 20 pruriginous lesions at screening and Day 1.

Note: Pruriginous lesions may include nodules, papules, plaques, umbilicated ulcers, or ulcers.

6. Pruriginous lesions on ≥ 2 different body regions at screening and Day 1.

Note: Pruriginous lesions may include nodules, papules, plaques, umbilicated ulcers, or ulcers.

- 7. IGA score \geq 3 at screening and Day 1.
- 8. Pruritus as defined by the following:
 - a. Screening: Itch NRS score \geq 5 based on recall for the week preceding screening.
 - b. Day 1: Average Itch NRS \geq 5 for the week before Day 1. Note: Participants must have at least 4 nonmissing Itch NRS daily scores out of the 7 days before Day 1 to calculate an average and be randomized.
- 9. Willingness to avoid pregnancy or fathering children based on the criteria below.
 - a. Male participants with reproductive potential must agree to take appropriate precautions to avoid fathering children from screening through 90 days (a spermatogenesis cycle) after the last dose of study drug and must refrain from donating sperm during this period. Permitted methods in preventing pregnancy (see Appendix A) should be communicated to the participants and their understanding confirmed.
 - b. Female participants who are not of childbearing potential or, if of childbearing potential, must have a negative pregnancy test at screening (serum) and before the first dose on Day 1 (urine). Women of childbearing potential must agree to take appropriate precautions to avoid pregnancy from screening through 30 days (1 menstrual cycle) after the last dose of study drug and must refrain from donating oocytes during this period. Permitted methods in preventing pregnancy (see Appendix A) should be communicated to the participants and their understanding confirmed.

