10.4.1. Primary Analysis

The primary analysis will be based on the ITT population. The primary alternative hypothesis (superiority of the INCB054707 groups compared with the placebo group for the proportion of participants achieving \geq 4-point improvement in Itch NRS score at Week 16) will be tested using exact logistic regression (Mehta and Patel 1995). This model will include the treatment groups and stratification factor. The unadjusted p-values between each of the INCB054707 groups and the placebo group will be compared with the prespecified significance level. Odds ratio and corresponding 95% CI will be provided as well. All nonresponders in the placebo-controlled period, as well as all participants who are missing postbaseline values, will be defined as nonresponders for the nonresponder imputation analysis. All participants who receive rescue therapy during the placebo-controlled period will be imputed as nonresponders.

The endpoint of different active doses versus placebo will be tested in a fixed sequence from high to low (75 mg, 45 mg, and 15 mg) at 2 sided $\alpha = 0.5$ level. The lower dose will be tested only if the statistical hypothesis associated with the higher dose is rejected.

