3.2. Control of Type I Error

The overall significance level for efficacy analysis will be 0.05 for 2-sided tests.

A set of hypotheses corresponding to the treatment comparisons between povorcitinib 15, 45, or 75 mg and placebo will be tested in fixed sequential:

- H1: Povorcitinib 75 mg is not equal to placebo in achieving ≥ 4-point improvement in Itch NRS score at Week 16
- H2: Povorcitinib 45 mg is not equal to placebo in achieving ≥ 4-point improvement in Itch NRS score at Week 16
- H3: Povorcitinib 15 mg is not equal to placebo in achieving ≥ 4-point improvement in Itch NRS score at Week 16

Hypothesis 2 will only be tested if H1 is rejected; testing for H3 will be implemented only if H1 and H2 are rejected.

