3.3. Sample Size Considerations

In order to provide a safety database and adequate power for efficacy analysis, the total sample size for the study is 140 participants randomized in a 1:1:1:1 ratio to povorcitinib 15, 45, or 75 mg or placebo groups and stratified by IGA score on Day 1 (3 vs 4). The sample size calculation is based on Fisher's exact test for the statistical comparison on the primary efficacy endpoint, ie, the proportion of participants achieving \geq 4-point improvement in Itch NRS at Week 16. Based on the results from a Phase 2 trial of nemolizumab (Stander et al 2020), the response rate is assumed to be 50% for the povorcitinib 45 and 75 mg groups and 15% for the placebo group. Using a 2-sided alpha of 0.05, 35 participants per group will have 85% power to detect such a difference between either one of the 3 active treatment groups and the placebo group.

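### The primary analysis makes no use of baseline Itch NRS, the score from which response is measured; the planned test is valid and keeps its power, but a supportive analysis adjusted for baseline itch should be prespecified

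*SAP*

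**What the plan says.** **Model.** SAP 7.4.1 compares 75 mg with placebo by exact logistic regression in the ITT population: "This model will include the treatment groups (placebo and povorcitinib 15, 45, and 75 mg) and stratification factor". Protocol 10.4.1 agrees: "This model will include the treatment groups and stratification factor". The only stratification factor is Day 1 IGA, 3 versus 4. SAP 7.1 carries the randomization strata into all efficacy analyses unless something else is stated, so a further covariate is possible if it is specified.

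**What IGA measures.** SAP 7.2.1 and Protocol 8.2.2 grade IGA by the number of lesions. It does not measure itch.

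**Endpoint and baseline.** SAP 7.2.4.1 uses a 0-10 scale, a 4-point fall as the response threshold, and this baseline: "The baseline Itch NRS score will be determined by averaging the 7 daily Itch NRS scores before Day 1". Protocol 5.1 requires a Day 1 weekly average of at least 5, with no upper limit, and makes the baseline a condition of randomization: "Participants must have at least 4 nonmissing Itch NRS daily scores out of the 7 days before Day 1".

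**Other analyses.** The subgroups in SAP 7.4.2 are age, sex, region and baseline IGA. SAP 7.4.3, on sensitivity and supportive analyses of the primary endpoint, is marked not applicable. Appendix A adds an observed-values figure, which does not bear on baseline itch.

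**Power.** SAP 3.3: "The sample size calculation is based on Fisher's exact test for the statistical comparison on the primary efficacy endpoint", and "the response rate is assumed to be 50% for the povorcitinib 45 and 75 mg groups and 15% for the placebo group".

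**The concern.** A fixed 4-point threshold asks different things of different participants. The required proportional fall is 4 / baseline:

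- baseline 5: 4/5 = 80%, down to 1 or below
- baseline 8: 4/8 = 50%, down to 4 or below
- baseline 10: 4/10 = 40%, down to 6 or below

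Baseline itch is therefore a natural candidate to predict response, more so than a lesion count. Two things follow if it does. An analysis that uses it has somewhat more power than one that does not. And a chance difference in mean baseline between the 75 mg and placebo arms moves the odds ratio, with nothing in the plan to show by how much. The second matters most for 75 mg versus placebo, because the 45 mg and 15 mg tests follow only if that comparison succeeds (SAP 3.2).

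**Working it through.** **1. The plan's own figure.** Inputs from SAP 3.3: 35 per group, 50% versus 15%, two-sided alpha 0.05, Fisher's exact test. Power is the sum of Bin(x; 35, 0.50) × Bin(y; 35, 0.15) over all (x, y) with Fisher p ≤ 0.05. Result: 85.2%. The stated 85% reproduces.

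**2. What has to be assumed.** The documents give neither the distribution of baseline itch nor its link with response. Two baseline distributions were used, both normal and truncated to 5-10: A (mean 8, SD 1.2) and B (mean 7.5, SD 2). Two forms of dependence were used:

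- Logistic: logit P(response) = a(arm) + g × (baseline − mean), with a(arm) solved so that the overall rates stay at 50% and 15%.
- Percent reduction: response if baseline × R ≥ 4, with R normal (SD 0.35 or 0.20, limited to −0.5 to 1) and its mean solved for the same overall rates.

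IGA was simulated as non-prognostic. Each scenario had 4,000 trials of 75 mg versus placebo, 35 per arm. The exact conditional test was stratified by IGA, or by IGA × baseline itch split at the median. The standard error of one simulated power is √(0.85 × 0.15 / 4000) = 0.6 points; both tests were run on the same trials, so their differences are steadier.

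**3. Power (%) of the exact test.**

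| Dependence | Baseline | 75 mg response, lower to upper quartile of baseline | IGA only | IGA × itch | Gain |
|---|---|---|---|---|---|
| g = 0 | A / B | 50 to 50 / 50 to 50 | 85.3 / 85.5 | 86.6 / 86.8 | 1.3 / 1.3 |
| g = 0.25 | A / B | 45 to 55 / 43 to 57 | 86.4 / 84.8 | 87.6 / 86.6 | 1.2 / 1.8 |
| g = 0.5 | A / B | 41 to 60 / 37 to 63 | 85.1 / 85.6 | 87.0 / 88.5 | 1.9 / 2.9 |
| g = 1.0 | A / B | 32 to 69 / 26 to 75 | 86.2 / 85.8 | 90.9 / 91.4 | 4.7 / 5.6 |
| Percent reduction, SD 0.35 | A / B | 45 to 56 / 42 to 59 | 86.2 / 85.6 | 87.7 / 87.9 | 1.5 / 2.3 |
| Percent reduction, SD 0.20 | A / B | 41 to 61 / 35 to 66 | 85.2 / 84.9 | 87.5 / 88.6 | 2.3 / 3.7 |

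The IGA-only test stays at about 85-86% throughout. The 1.3 points gained at g = 0 carry no prognostic information: a finer stratification makes the exact test less conservative.

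**4. Cross-checks.** A score test with baseline itch as a continuous covariate changes power by −0.4 to +0.5 points at g = 0 to 0.25, +0.7 to +2.0 at 0.5 and +3.1 to +5.0 at 1.0. A simulation closer to the planned four-arm model (additive IGA and itch factors, 2,800 trials per scenario, 15 mg rate assumed 30%) gives gains of 1.7 at g = 0, 2.7 at 0.25, 3.0 at 0.5 and 2.4-2.6 under percent reduction.

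**5. Type I error** (both arms at 15%; g = 0, 0.5, 1.0). IGA only: 2.1-2.4%. IGA × itch: 3.0-3.6%.

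**6. Chance imbalance.** The SD of the between-arm difference in mean baseline is the SD of baseline × √(2/35) = SD × 0.239. In the simulations it was 0.24-0.32 points. An adverse difference beyond 1.5 SD has probability of about 1 − Φ(1.5) = 6.7% and averages about 0.5 points. Power of the IGA-only test, distribution A, 12,000 trials:

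| g | Adverse, beyond 1.5 SD | Within 0.5 SD of balance | Favourable, beyond 1.5 SD |
|---|---|---|---|
| 0.5 | 75.9% | 85.8% | 93.4% |
| 1.0 | 62.7% | 86.8% | 96.6% |

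Under the null, the two-sided rejection rate given such an imbalance is 0.6 + 2.4 = 3.0% (adverse) and 1.5 + 0.4 = 1.9% (favourable) at g = 0.5; at g = 1.0 it is 0.1 + 4.5 = 4.6% and 3.7 + 0.3 = 4.0%.

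**The case against.** The case for leaving the plan alone is substantial. Protocol and SAP name the same model, which uses exactly the stratification factor, and nothing in it is invalid. The sample size was set on an unadjusted test, so no promised power is missing. Part of the apparent gain comes from the discreteness of the exact test. The 80% versus 40% contrast matters only if itch falls roughly in proportion to its starting level, which the documents do not establish. Randomization makes imbalance equally likely in either direction. Changing the primary model would depart from Protocol 10.4.1, add a dichotomized covariate and change the odds ratio. Baseline is not guaranteed either: SAP 7.2.4.1 provides for a missing value, and Protocol 7.1.1 foresees participants later found ineligible.

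All of this stands against two stronger readings that a reader might infer: that the primary test is underpowered because of the omission, or that imbalance makes it invalid. Steps 3, 5 and 6 support neither. It also weighs against insisting on a new primary model.

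It does not answer the narrower point. A two-level factor enters exact logistic regression as IGA does, so computation is no obstacle, and a supportive analysis leaves the primary test and the fixed sequence untouched. Parts of the SAP between Sections 7.5 and 9 are not visible, and the baseline list in 6.1.2 is open-ended, so it cannot be said that baseline itch goes untabulated. Sections 7.4.1 to 7.4.3 are visible, however, and none of them uses it for the primary endpoint.

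**Conclusion.** The point holds as a modest, inexpensive improvement and not as an error. The planned test is valid and has its stated 85% power. The plan forgoes about 1-4 points of power under weak to moderate dependence and about 5-6 under strong dependence. About 1 point of this is reduced conservatism of the exact test (1.3 in the pairwise simulation, 1.7 in the four-arm check).

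The better reason to act is interpretation. An adverse baseline difference of about 0.5 points is uncommon, but with moderate to strong dependence it could decide whether the sequence opens, and a favourable one could flatter the 75 mg result. The plan has no prespecified way to examine either. This is a matter of precision and of reading the estimate; type I error stays below 5% even given such an imbalance.

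All sizes depend on the assumed baseline distributions and slopes. If response does not depend on baseline itch, only the discreteness gain remains.

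**What to change.** In SAP 7.4.3, replace the not-applicable entry with a supportive analysis that repeats the 7.4.1 model with baseline Itch NRS category as a second class factor: below versus at or above the blinded pooled median. Fix the cutpoint before unblinding; if that is no longer possible, label the analysis post hoc. State a rule for a missing baseline, for example assignment to a category named in advance, so that no ITT participant drops out of the model. Add the same category to the subgroups in 7.4.2.

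If the sponsor prefers to put the factor in the primary model, SAP 11.1, which now declares no changes, should record it as a change from Protocol 10.4.1.

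The cost is one more analysis from data already collected. The adjusted odds ratio is conditional on itch category as well as IGA and should not be read as the same quantity. As a guide, the unadjusted log odds ratio at the planning rates is ln[(0.50/0.50) / (0.15/0.85)] = 1.73, against 2.07-2.26 conditional on continuous baseline itch at g = 1.0.

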7.4.2. Subgroup Analyses for Primary Endpoint

Subgroups will be formed based on the following participant characteristics and baseline variables for those participants whose data are available:

- Age group (< 65 and \geq 65 years)
- Gender (male, female)
- Geographical region
- Baseline IGA (3 vs 4)

The primary efficacy endpoint will be summarized using descriptive statistics based on the ITT population for the aforementioned subgroups.

7.4.3. Sensitivity and Supportive Analyses for Primary Endpoint

Not applicable.

7.5. Analysis of the Secondary Efficacy Parameters

The secondary efficacy endpoints include the proportion of participants achieving IGA-TS at Week 16 and the time it takes to achieve $a \ge 4$ -point improvement from baseline in the Itch NRS score.

The proportion of participants achieving IGA-TS at Week 16 will be summarized using descriptive statistics. The NRI approach will be used to address initiation of rescue medication, treatment discontinuation, and missing data.

For the time to \geq 4-point improvement from baseline in Itch NRS score during the PC period, Kaplan-Meier curves will be presented by treatment groups. The number of participants, number of events, and number of censoring events will be summarized by treatment groups. The Kaplan-Meier estimate of median time will be presented with its 95% CI. The 95% CI will be calculated using the method by Brookmeyer and Crowley (1982).

